## 6.2 SUMMARIES OF CONDUCT OF STUDY

The number of patients who enroll, discontinue, or complete the study will be summarized. Reasons for patient discontinuations from the study treatment and from the study will be listed and summarized. Enrollment, study treatment administration, and major protocol deviations will be described, listed, or summarized and evaluated for their potential effects on the interpretation of study results.

### **6.3 SUMMARIES OF DEMOGRAPHIC AND BASELINE CHARACTERISTICS**

Demographic and baseline characteristics such as age, sex race/ethnicity, weight, type of malignancy, and baseline ECOG performance status will be summarized using means, standard deviations, medians, and ranges for continuous variables and proportions for categorical variables, as appropriate. Concomitant medications received during the treatment period will be summarized.

### **6.4 EFFICACY ANALYSES**

Efficacy analyses will include all evaluable patients, defined as all patients who receive any amount of study treatment.

#### **6.4.1 Primary Efficacy Endpoint for Patients with Prostate Cancer**

For patients with prostate cancer, PSA response rate is defined as the proportion of patients achieving a PSA decline  $\geq 50\%$  from baseline. Patients without a post-baseline PSA assessment will be considered non-responders. The PSA response rate will be calculated, and the 95% CI will be estimated using the Clopper-Pearson method.

#### **6.4.2 Secondary Efficacy Endpoints for Patients with Prostate Cancer**

For patients with prostate cancer, an objective response is defined as a CR or PR on two consecutive occasions  $\geq 4$  weeks apart, according to RECIST v1.1 and PCWG3 criteria, in patients with measurable disease at baseline. Patients without a post-baseline tumor assessment will be considered non-responders. ORR is defined as the proportion of patients who have an objective response in patients with measurable disease at baseline. ORR will be calculated, and the 95% CI will be estimated using the Clopper-Pearson method.

Among patients with an objective response (responders), DOR will be defined as the time from first occurrence of a documented objective response until the time of documented disease progression or death from any cause during the study, whichever occurs first. For patients who do not have documented disease progression or death during the study, DOR will be censored at the day of the last evaluable tumor assessment.

rPFS is defined as the time from study treatment initiation to the first occurrence of documented disease progression, as assessed by the investigator with use of the PCWG3 criteria (soft tissue by CT or MRI scans according to RECIST v1.1, and bone metastasis by bone scan according to the PCWG3 criteria) or death from any cause, whichever occurs first. For patients who do not have documented disease progression or death during the study, rPFS will be censored at the day of the last evaluable tumor assessment.

OS will be defined as the time from study treatment initiation to the time of death due to any cause. For patients who do not have death during the study, OS will be censored at the last known alive date.

Kaplan-Meier methodology will be used to estimate the median rPFS, DOR, and OS, and the Kaplan-Meier curves will be provided. The Brookmeyer-Crowley method will be used to construct the 95% CI for each median.

#### **6.4.3 Exploratory Efficacy Endpoints**

Additional exploratory analyses will evaluate treatment effect in additional biomarker-defined segments (e.g., *PTEN*-loss) within prostate cancer in Part 2.

### **6.5 SAFETY ANALYSES**

The safety analyses will include all patients who received at least one dose of any study drug, and will be analyzed and summarized separately for the Part 1 and Part 2; data will not be combined across phases.

Adverse events, deaths, change in laboratory test results, change in vital signs, and exposure to components of study treatment will be assessed to determine the safety of treatment regimen.

For safety-evaluable patients, study drug administration data will be tabulated or listed by arm, and any dose modifications will be flagged. Descriptive statistics will be used to summarize the total dose of ipatasertib and rucaparib received.

Verbatim descriptions of adverse events will be mapped to appropriate thesaurus terms. All adverse events occurring on or after treatment Day 1 will be summarized by the mapped term, appropriate thesaurus levels, and NCI CTCAE v5.0 toxicity grade. In addition, adverse events leading to treatment withdrawal or death, and serious adverse events will be listed with more detailed information, such as the day of onset of an adverse event, duration of adverse event, toxicity grade, and so on.

Relevant laboratory and vital signs (heart rate, blood pressure, and temperature) and ECG data will be displayed by time post-dose, with NCI CTCAE Grade 3 and 4 values identified where appropriate. Additionally, changes in laboratory data will be summarized by grade using the NCI CTCAE toxicity grade. Selected vital signs and selected laboratory data will be summarized by visit.

The extent of study drug exposure (dose and duration) will be examined to determine the degree of treatment tolerability. In addition to study treatment duration and total dose received, any dose modification of study drugs will also be summarized.

## 6.6 PHARMACOKINETIC ANALYSES

For Part 1, plasma samples for PK characterization of ipatasertib, its metabolite G-037720, and rucaparib will be collected on Day 1 of Cycle 1 for ipatasertib and G-037720, Day 15 of Cycle 1, and Days 1 and 15 of Cycle 2 (ipatasertib, G-037720, and rucaparib). For ipatasertib, the sampling will allow for determination of the total exposure (area under the concentration–time curve from Time 0 to Time t [AUC0–t]) and the time to achieve maximum concentration ( $T_{max}$ ), and maximum concentration ( $C_{max}$ ) at steady state as a single agent (baseline) and in the presence of rucaparib. For rucaparib, the sampling will allow for determination of predose trough concentrations. Any effect of rucaparib on ipatasertib, or its metabolite G-037720, will be evaluated by comparing the *pharmacokinetics of ipatasertib in combination with rucaparib* on Day 15 of Cycle 1 to *monotherapy pharmacokinetics with Day 1 of Cycle 1 after the single-agent run-in phase*. Mean and individual concentration–versus-time graphs will be plotted, and PK parameters will be tabulated and summary statistics reported for all analytes. Other PK parameters may be determined as data allow. Potential correlations of relevant PK parameters with dose, safety or efficacy outcomes, and other covariates may be explored.

For Part 2, trough samples of ipatasertib, G-037720, and rucaparib will be collected on Day 15 of Cycle 1 and on Days 1 and 15 of Cycle 2 to confirm comparability to Part 1 trough and/or historical data in a descriptive manner.

Any remaining PK samples after evaluation of ipatasertib, G-037720, and rucaparib may be used for exploratory evaluation of other analytes related to the administered drugs or biomarkers, enzymes, and transporters affecting their disposition *or safety profile*.

Additional PK analyses will be conducted as appropriate.

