- Sections 5.1.1 and 5.1.2 were updated for consistency with the identified risks and reported adverse events in the current version of the Rucaparib Investigator's Brochure.

- Section 5.1.4.4, Table 6, has been revised to replace any reference to hyperglycemia grading according to fasting glucose levels in the recommendations for the management of hyperglycemia.
- Section 5.1.4.6 has been revised to describe photosensitivity related to rucaparib and provide recommendation for prevention consistent with guidance in the Rucaparib Investigator's Brochure.
- Section 5.1.4.8, Table 10, has been updated to be consistent with National Cancer Institute Common Terminology Criteria for Adverse Events, Version 5, for hepatotoxicity.
- Section 5.4.3.3 has been amended regarding the reporting of spontaneous abortions and therapeutic or elective abortions performed because of an underlying maternal or embryofetal toxicity as serious adverse events.
- Section 6.6 and Appendix 2 have been updated for additional pharmacokinetic assessments to better define potential drug–drug interactions between ipatasertib and rucaparib.
- Section 10, References, has been revised.
- An error with a sampling timepoint in Appendix 2 has been corrected. The Cycle 1, Day 1 timepoint has been revised to Cycle 1, Day –7. A clarification has also been added in the footnote that the PK sample is for analysis of coproporphyrin I (CPI) and CPIII levels at baseline as described in Section 3.3.4.

Additional minor changes have been made to improve clarity and consistency. Substantive new information appears in italics. This amendment represents cumulative changes to the original protocol.

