#### **4.3.2.2 Rucaparib**

Patients will self-administer oral rucaparib BID (approximately 12 hours apart) at the cohort-assigned dose throughout the treatment period unless dose reduction is required for adverse event management. *In Part 1 only, patients will start rucaparib on the evening of Day 1 of Cycle 1 following all PK sampling of ipatasertib on that day.* Patients should take rucaparib as directed by the treating physician. Patients may take *rucaparib with or without food. Rucaparib may be taken concurrently with ipatasertib on days when the patient is taking both.* Each dose should be taken with at least 8 ounces (240 mL) of water.

Tablets should be swallowed whole. Missed doses (i.e., patient does not take dose within 6 hours of the scheduled time) or vomited doses will not be made up; the patient should resume rucaparib dosing with the next scheduled dose.

On PK sampling days, patients will be instructed not to administer rucaparib study drug at home but to bring their bottles of rucaparib and their dosing diaries to the clinic. Patients will be instructed when to take their doses of rucaparib in the clinic in the context of the schedule of activities for the given visit. Time of dose administration will be collected on the PK sampling day and for prior doses administered *the day* before a PK sampling visit. Any incidence of vomiting within 3 hours after drug administration should also be recorded for the day of PK sampling. A sufficient amount of rucaparib should be provided to the patient to last one treatment cycle. Patients will be instructed to bring their bottles of rucaparib and their medication diaries to each study visit.

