## **6. STATISTICAL CONSIDERATIONS AND ANALYSIS PLAN**

The primary analysis will be based on patients data collected through study discontinuation or at the end of study. All analyses will be conducted using the safety-evaluable population, defined as all patients who receive any amount of study treatment.

No formal hypothesis testing is planned. The safety, tolerability, clinical activity, and pharmacokinetics of ipatasertib, and its metabolite G-037720, with rucaparib will be described and summarized.

Data will be described and summarized as warranted by sample size. That is, listings may be used in lieu of tables in the event of small sample size.

Descriptive statistics will be used to summarize the safety and clinical activity of treatment regimens. Continuous variables will be summarized using means, standard

deviation, median, and range; categorical variables will be summarized using count and percentage.

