### Schedule of Pharmacokinetic Samples (Parts 1 and 2)

**Table 1 Schedule of Pharmacokinetic Samples in Dose-Escalation Phase (Part 1)**

Visit	Timepoint	Sample Type
Cycle 1, Day -7 a	Prior to first ipatasertib administration	Ipatasertib PK (Plasma)
Cycle 1, Day 1 b	1 hour ( $\pm$ 10 min) post-ipatasertib dose	Ipatasertib PK (Plasma)
	2 hour ( $\pm$ 10 min) ipatasertib post-dose	Ipatasertib PK (Plasma)
	3 hour ( $\pm$ 30 min) ipatasertib post-dose	Ipatasertib PK (Plasma)
	5 hour ( $\pm$ 30 min) ipatasertib post dose	Ipatasertib PK (Plasma)
Cycle 1, Day 15 c	Prior to ipatasertib and rucaparib administration	Ipatasertib PK (Plasma) Rucaparib PK (Plasma)
	1 hour ( $\pm$ 10 min) post-ipatasertib dose	Ipatasertib PK (Plasma)
	2 hour ( $\pm$ 10 min) post-ipatasertib dose	Ipatasertib PK (Plasma)
	3 hour ( $\pm$ 30 min) post-ipatasertib dose	Ipatasertib PK (Plasma)
	5 hour ( $\pm$ 30 min) post-ipatasertib dose	Ipatasertib PK (Plasma)
Cycle 2, Day 1 c	Prior to ipatasertib and rucaparib administration	Ipatasertib PK (Plasma) Rucaparib PK (Plasma)
Cycle 2, Day 15 c	Prior to ipatasertib and rucaparib administration	Ipatasertib PK (Plasma) Rucaparib PK (Plasma)

*CPI = coproporphyrin I; CP III = coproporphyrin III; PK = pharmacokinetic.*

*Note: Ipatasertib PK samples will be collected for analysis of both ipatasertib and its metabolite G-037720.*

- a The Cycle 1, Day -7 assessment should be done prior to start of ipatasertib and rucaparib administration. The sample will be used for measurement of baseline CPI and CP III levels prior to treatment initiation.
- b PK sampling on Day 1 of Cycle 1 should be completed before initiation of rucaparib therapy.
- c If a patient's ipatasertib or rucaparib treatment has been interrupted for  $\geq$  1 day immediately before the Cycle 1, Day 15 and Cycle 2 visits, PK samples may be rescheduled to another day when both study treatments have been given for at least 5 consecutive days. Cycle 1, Day 15 and Cycle 2 visit assessments during the treatment period should be performed within  $\pm$  7 days of the scheduled date. Study assessments may be delayed or moved ahead of the window to accommodate holidays, vacations, and unforeseen delays.

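### Section 6.6 promises a single-agent ipatasertib AUC from Time 0, but Appendix 2 schedules no pre-dose sample on Cycle 1 Day 1, so that value can only be modelled or imputed

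*Combined protocol and SAP*

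**What the plan says.** Section 6.6 (Pharmacokinetic Analyses) says of Part 1: "For ipatasertib, the sampling will allow for determination of the total exposure". It defines this as the area from Time 0 to Time t, adds Tmax and Cmax, and places all three "at steady state as a single agent (baseline) and in the presence of rucaparib". It evaluates any effect of rucaparib on ipatasertib or its metabolite G-037720 by comparing Cycle 1 Day 15 with Cycle 1 Day 1, the latter being the monotherapy reference after the 7-day run-in.

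Appendix 2 Table 1 sets the sampling times. Day 15 opens with a sample labelled "Prior to ipatasertib and rucaparib administration", followed by 1, 2, 3 and 5 h. Day 1 has 1, 2, 3 and 5 h only. The one earlier sample is on Day -7, before any ipatasertib. Its footnote says "The sample will be used for measurement of baseline CPI and CP III levels prior to treatment initiation". Another footnote says "PK sampling on Day 1 of Cycle 1 should be completed before initiation of rucaparib therapy", and Section 4.3.2.2 agrees that in Part 1 "patients will start rucaparib on the evening of Day 1 of Cycle 1 following all PK sampling of ipatasertib on that day".

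Section 3.3.4 allows non-compartmental analysis, population PK or both, and comparison with single-agent data from other trials. Section 6 states "No formal hypothesis testing is planned".

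**The concern.** The reference day of the named comparison lacks the sample at which the stated AUC begins. Time 0 on Day 1 follows seven daily doses (Day -7 to Day -1), so it cannot be taken as zero. Section 3.3.1 itself treats this day as steady state.

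The run-in exists to make this comparison. Section 3.3.1 expects that rucaparib may raise ipatasertib exposure through CYP3A inhibition and says the data will help in determining the recommended Phase II dose. Section 3.1.4 has the available PK data reviewed before Part 2 opens. With no rule for Time 0 on Day 1, the analyst's choice shifts the reported ratio. With no monotherapy trough, nothing measured shows the end of the dosing interval on ipatasertib alone.

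**Working it through.** The plan gives no figure to reproduce here. The check compares the schedules and then sizes the gap.

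**Step 1: which samples exist (Appendix 2 Table 1).**

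| Part 1 visit | Ipatasertib samples | Drug state |
|---|---|---|
| Cycle 1 Day -7 | before first dose | no drug yet |
| Cycle 1 Day 1 | 1, 2, 3, 5 h | ipatasertib alone |
| Cycle 1 Day 15 | pre-dose, 1, 2, 3, 5 h | combination |
| Cycle 2 Days 1 and 15 | pre-dose | combination |

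Time 0 is the only Day 15 time missing on Day 1. Every scheduled pre-dose sample is taken either before any ipatasertib or on the combination. The G-037720 values come from the same tubes.

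**Step 2: weight of Time 0.** Linear-trapezoid weights at 0, 1, 2, 3 and 5 h are 0.5, 1, 1, 1.5 and 1, which sum to 5. Time 0 carries 0.5/5 = 10%. With m the weighted mean of the 1-5 h values, AUC0-5 = 0.5 × C0 + 4.5 × m.

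**Step 3: sensitivity to handling when there is no interaction.** If C0 is counted on Day 15 but set to zero on Day 1, the ratio is (0.5 × C0 + 4.5 × m)/(4.5 × m) = 1 + r/9, where r = C0/m. The documents do not give r, so I assume a range:

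| r | 0.1 | 0.3 | 0.5 | 0.8 | 1.0 |
|---|---|---|---|---|---|
| null ratio | 1.011 | 1.033 | 1.056 | 1.089 | 1.111 |

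Other handlings move it differently. Take a flat profile at 1 from 1 to 5 h with C0 = 0.3 on both days:
- True AUC0-5 = 0.15 + 4.5 = 4.65.
- Day 1 C0 set to zero: 4.65/4.5 = 1.033.
- Day 1 C0 set to the lowest observed value: 4.65/5 = 0.930.
- Day 15 AUC0-5 against Day 1 AUC1-5: 4.65/4 = 1.163.
- AUC1-5 on both days: 4/4 = 1.000.

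Over three assumed shapes (flat, early peak, late peak) with C0 at 5% to 50% of Cmax, the ranges are 1.006-1.071 for zero, 0.905-1.000 for lowest observed and 1.09-1.25 for mixed intervals.

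**Step 4: what the existing samples and an added one can show.** I assume a one-compartment oral model with 24-h dosing, half-life 12-48 h and ka 0.7-1.5/h. The documents give none of these values. At steady state, C(t) is proportional to ka/(ka - k) × [exp(-kt)/(1 - exp(-24k)) - exp(-ka·t)/(1 - exp(-24ka))], with k = ln 2/half-life. An interaction that multiplies 24-h AUC by R lowers k to k/R. The approximate AUC0-24 is AUC0-5 + 19 × (C5 + C0)/2, using the pre-dose value as the 24 h value.

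| True 24-h ratio R | AUC1-5 ratio | Approximate AUC0-24 ratio | AUC0-5 ratio minus AUC1-5 ratio |
|---|---|---|---|
| 1.25 | 1.16-1.23 | 1.22-1.25 | 0.006-0.014 |
| 1.5 | 1.31-1.46 | 1.45-1.50 | 0.012-0.028 |
| 2.0 | 1.63-1.91 | 1.91-2.00 | 0.025-0.058 |

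At R = 2.0 the AUC0-5 ratio is 1.67-1.94. Adding Time 0 to the 0-5 h window therefore changes little. Stopping at 5 h costs more: AUC1-5 can fall short by 2.0 - 1.63 = 0.37. The main gain from a Day 1 pre-dose sample is that it allows the 24-h approximation on both days. On a wider grid (half-life 4-48 h, ka 0.5-2/h) the last column can be slightly negative, from -0.004 at R = 1.25, so its sign is not guaranteed.

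**The case against.** The strongest reply is that Section 6.6 says the sampling allows the AUC to be determined, without saying non-compartmentally or from a measured Time 0. Section 3.3.4 names population PK, and a model fitted to the dosing records and the four Day 1 samples can return an AUC from Time 0. This stands in part. A reader might infer that the single-agent AUC cannot be obtained at all, and the documents do not support that. What remains is that it would be modelled rather than observed, that Section 6.6 does not say so, and that the two days would rest on different evidence. The allowance in Section 6.6 for further PK analyses does not supply a sample that was never drawn.

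A reader might also infer that the interaction assessment fails or that the dose decision is compromised. Neither follows. Cmax, Tmax and AUC1-5 can be compared as scheduled. No hypothesis is tested. Section 3.1.1.1 declares the recommended Phase II dose on dose-limiting toxicities and an acceptable safety profile, and no primary endpoint uses these concentrations.

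The Version 2 rationale says of an Appendix 2 timepoint: "The Cycle 1, Day 1 timepoint has been revised to Cycle 1", Day -7. A reader might infer that a Day 1 trough was removed by mistake. The rationale presents the change as correcting an error and identifies the sample as the coproporphyrin baseline. It gives no evidence of a lost trough, only that the Day -7 row is not a mislabelled Day 1 sample.

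Finally, since AUC1-5 is observed on both days and lies close to AUC0-5, a reader might make it the common metric and stop there. Closeness to AUC0-5 is not closeness to 24-h exposure, as Step 4 shows.

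**Conclusion.** The mismatch is real. Section 6.6 and Appendix 2 Table 1 disagree about what can be observed on the reference day, for ipatasertib and for G-037720. It is worth correcting, but small: in the assumed one-compartment model (r of 0.31-0.77), setting Day 1 Time 0 to zero would turn a null ratio into 1.034-1.085, and the plan proposes no such rule. The more useful loss is the monotherapy trough, and with it any observed basis for 24-h exposure on ipatasertib alone.

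The finding about the schedule rests on the documents alone. The sizes rest on assumed profiles and kinetics. The 24-h approximation also needs Day 1 to be near steady state. With a 48 h half-life, the Day 1 pre-dose level would be 1 - 0.5^(168/48) = 91% of steady state. That limit is separate from the missing sample.

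**What to change.** Preferred: add a row to Appendix 2 Table 1, *Cycle 1, Day 1: prior to ipatasertib administration: Ipatasertib PK (Plasma)*. Then calculate AUC0-5, the pre-dose ratio and, if steady state is accepted, the approximate AUC0-24 in the same way on both days for ipatasertib and G-037720. The cost is one extra tube in up to about 24 Part 1 patients, fewer if some have already passed that visit (enrolment status is not given). Section 4.3.2.1 already has patients take their ipatasertib in the clinic on PK days. Because Appendix 1 footnote s ties non-fasting glucose draws to the ipatasertib PK times, say whether the new time adds one. That footnote's pointer to Appendix 3 instead of Appendix 2 is a separate clerical matter.

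If the sample is not added, and for patients who lack it, restate Section 6.6: *The single-agent AUC from Time 0 will be model-based (population PK). Non-compartmental comparison of Cycle 1 Day 15 with Cycle 1 Day 1 is limited to Cmax, Tmax and the 1-5 h interval observed on both days. A 1-5 h ratio can understate a change in 24-h exposure.* This costs wording only, but leaves no monotherapy trough. In neither case should AUC1-5 become the required common metric.

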### **3.3 RATIONALE FOR STUDY DESIGN**

#### **3.3.1 Rationale for Study Treatment Dose and Schedule**

Based on preclinical and limited clinical studies, the combination of ipatasertib and rucaparib may have synergistic anti-tumor activity. This study is designed to assess the safety and preliminary efficacy of the two drugs in combination.

The starting dose for ipatasertib in Part 1 will be 300 mg PO QD, and the starting dose for rucaparib in Part 1 will be 400 mg PO BID. The highest potential dose for ipatasertib is 400 mg QD, which is the current dose of ipatasertib being studied in combination with abiraterone in prostate cancer and with paclitaxel in breast cancer. Ipatasertib is given continuously with abiraterone; it is given for 21 days of every 28-day cycle with paclitaxel. The highest potential dose for rucaparib is 600 mg BID *given continuously*, which is the approved dose for rucaparib monotherapy. Since ipatasertib has not been administered with rucaparib before, the Dose-Escalation Phase includes different dose combinations in cohorts of approximately 6 patients each. Additional dose de-escalation levels for ipatasertib or rucaparib (or both) may be explored during Part 1 if the frequency of DLT is > 33%.

In Part 1, there is a 7-day run-in period for ipatasertib alone prior to Cycle 1. The rationale for the run-in is to allow for PK *assessment* of ipatasertib monotherapy *after the run-in phase for comparison with the pharmacokinetics* in combination with rucaparib. Based on available information to date, there could be a potential for increased exposure to ipatasertib when given in combination with rucaparib *due to CYP3A inhibition by rucaparib*. PK sampling of ipatasertib monotherapy at steady-state and following addition of rucaparib at steady state will add to PK data for drug–drug interaction evaluation and aid in determining the RP2D for both agents when administered in combination. *Trough rucaparib concentrations will also be evaluated and compared with published single-agent data.*

Based on prior Phase I data with an AKT inhibitor combined with a PARP inhibitor (Westin et al. 2017), the overlapping toxicities are expected to be limited. Given the available clinical safety data, ipatasertib 300 mg QD and rucaparib 400 mg BID are considered appropriate starting doses to evaluate the combination.

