#### **3.3.4 Rationale for the Pharmacokinetic Evaluation Schedule**

Plasma samples for PK characterization of ipatasertib, its metabolite G-037720, and rucaparib, will be collected as outlined in [Appendix 2](#). The sampling schedule is designed to enable characterization of ipatasertib PK using non-compartmental analysis and/or population PK (popPK) methodology. In addition, the PK data will allow comparison of ipatasertib exposure with single-agent ipatasertib data from the Phase I clinical trial (Study PAM4743g) and with ipatasertib data from other trials to evaluate whether ipatasertib exposures are altered in combination with rucaparib, which is a mild CYP3A4 inhibitor.

Rucaparib is metabolized by CYP2D6 and to a lesser extent by CYP1A2 and CYP3A4. Given that ipatasertib is a mild-to-moderate inhibitor of CYP3A4 (see the Ipatasertib Investigator's Brochure) and is not an inhibitor of CYP2D6 and CYP1A2, ipatasertib is not expected to alter rucaparib exposure in a clinically significant manner. Therefore, only trough concentrations of rucaparib will be evaluated in this study and compared to historical data in the literature.

Prior to start of any drug treatment in Part 1, a PK biomarker sample may be collected to measure baseline levels of coproporphyrin (CP) I and III, which are putatively transported into the liver by uptake transporters OATP1B1 and OATP1B3.

The levels of these endogenous substrates of organic-anion-transporting polypeptide (OATP) transporters, if warranted, will be measured in an exploratory way prior to and on ipatasertib treatment to understand the impact of ipatasertib on OATP functionality. If the analysis is conducted, remaining plasma samples from PK analysis will be used for assessing on-treatment effect on CPI and CPIII levels.

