##### **4.3.2.1 Ipatasertib**

Patients will self-administer oral ipatasertib QD (approximately 24 hours apart) at the cohort-assigned dose throughout the treatment period unless dose reduction is required for adverse event management. Ipatasertib may be taken with or without food. *It may be taken concurrently with rucaparib on days when the patient is taking both.* If a dose is missed (i.e., not taken within 8 hours after the scheduled dosing time), the patient should resume dosing with the next scheduled dose. Missed or vomited doses will not be made up.

On PK sampling days, patients will be instructed not to administer ipatasertib study drug at home but to bring their bottles of ipatasertib and their dosing diaries to the clinic. Patients will be instructed when to take their doses of ipatasertib in the clinic in the context of the schedule of activities for the given visit. Time of dose administration will be collected on the PK sampling day and for prior dose administered *the day* before a PK sampling visit. Any incidence of vomiting within 3 hours after drug administration should also be recorded for the day of PK sampling. A sufficient amount of ipatasertib should

be provided to the patient to last one treatment cycle. Patients will be instructed to bring their bottles of ipatasertib and their medication diaries to each study visit.

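### Section 6.6 calls ipatasertib AUC0-t total exposure, but both interaction profiles stop at 5 hours of a 24-hour dosing interval, so the comparison rests on AUC0-5h and can misstate the interaction

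*Combined protocol and SAP*

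**What the plan says.** Section 6.6 names three ipatasertib parameters at steady state, alone and with rucaparib: AUC0-t, Tmax and Cmax. Of the first it says that "the sampling will allow for determination of the total exposure". The effect of rucaparib is to be judged by comparing Cycle 1 Day 15 (combination) with Cycle 1 Day 1 (monotherapy, after the run-in). Neither Section 6.6 nor the list of abbreviations gives a value for t, and there is no rule for extrapolating beyond the last sample.

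Appendix 2, Table 1, fixes the sampling times. Cycle 1 Day 1 has samples at 1, 2, 3 and 5 hours, the last being "5 hour ( $\pm$ 30 min) ipatasertib post dose". Cycle 1 Day 15 has a pre-dose sample and the same four times. On dosing, Section 4.3.2.1 says: "Patients will self-administer oral ipatasertib QD (approximately 24 hours apart) at the cohort-assigned dose".

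Section 3.3.1 expects that ipatasertib exposure may rise through CYP3A inhibition by rucaparib, and says that the PK sampling will "aid in determining the RP2D for both agents when administered in combination". Section 3.3.4 says that the schedule is meant to characterize ipatasertib "using non-compartmental analysis and/or population PK (popPK) methodology". Section 6.6 also leaves room for further PK parameters and analyses.

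**The concern.** An AUC that ends at the last sample covers the first 5 hours after the dose, not the dosing interval. The plan nevertheless labels it as total exposure and uses it in the comparison meant to show whether rucaparib raises ipatasertib levels.

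The window matters because of the suspected mechanism. Sections 3.3.3.3 and 4.4.2.1 say that ipatasertib is metabolized mainly by CYP3A, so a fall in systemic clearance is plausible. Slower clearance shows most in the later part of the curve, which is not sampled. A ratio of early partial AUCs can then come out closer to 1 than the ratio of full-interval exposures.

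The label carries a second risk. Section 3.3.4 plans comparisons with single-agent ipatasertib data from other trials. A 5-hour AUC reported as total exposure could be set against AUCs taken over a different window.

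**Working it through.** The plan states no figure for the share of exposure captured or for the size of the interaction, so there is none to reproduce.

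**Inputs from the documents.** Dosing interval 24 h (Section 4.3.2.1). Last sample at 5 h on both days (Appendix 2, Table 1). Run-in of 7 days (Section 3.1.1.1), so Day 1 is dose 8 and Day 15 is dose 22. Rucaparib starts on the evening of Day 1 (Section 4.3.2.2).

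**Inputs assumed, because the documents do not give them.** One compartment with half-life 8-48 h and absorption rate ka 0.7-1.5 per hour. Wider checks used half-life 6-48 h with ka 0.5-2 per hour, and two compartments with terminal half-life 18-30 h.

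**Step 1: clock share.** 5/24 = 20.8% of the interval. This needs no assumption.

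**Step 2: share of exposure.** For one compartment at steady state, with elimination rate k and dose and volume scaled to 1:

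- AUC0-24 = 1/k
- AUC0-5 = ka/(ka - k) × [(1 - e^(-5k)) / (k(1 - e^(-24k))) - (1 - e^(-5ka)) / (ka(1 - e^(-24ka)))]

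Example with half-life 8 h and ka = 1: k = 0.0866, AUC0-24 = 11.54, and AUC0-5 = 1.095 × (4.638 - 0.993) = 3.99. The share is 3.99/11.54 = 34.6%.

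**Step 3: the ratio when clearance falls.** Dividing k by R makes the true AUC0-24 ratio exactly R. In the example with R = 1.5, k = 0.0578 and AUC0-5 = 1.061 × (5.790 - 0.993) = 5.09. The observed ratio is 5.09/3.99 = 1.28, against a true 1.50.

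| Half-life (ka = 1) | Share in 0-5 h | True 1.5 reads | True 2.0 reads |
|---|---|---|---|
| 8 h | 34.6% | 1.28 | 1.56 |
| 12 h | 29.4% | 1.34 | 1.68 |
| 24 h | 24.7% | 1.42 | 1.83 |
| 48 h | 22.7% | 1.46 | 1.92 |

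Over ka 0.7-1.5 and half-life 8-48 h, the share is 22-37%, a true 1.5 reads 1.26-1.47, and a true 2.0 reads 1.54-1.93. The two-compartment cases give shares of 31-67%, with readings of 1.23-1.33 and 1.43-1.66. Across all models run, the share is about 22-67%.

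**Step 4: bioavailability only.** If rucaparib raises only the fraction absorbed, the whole curve scales. A true 1.5 reads 1.50, with no bias.

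**Step 5: the protocol's own schedule.** At a 48 h half-life, dose 8 has reached 1 - 2^(-192/48) = 1 - 1/16 = 93.75% of steady state. The Day 1 denominator is therefore too small: 1.458/0.9375 = 1.555. Allowing for Day 15 also being slightly short of its new steady state, the reading is 1.53-1.55 over ka 0.7-1.5. The direction has reversed for a 1.5-fold effect.

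**Step 6: can a trough supply the 24-hour value?** At steady state a pre-dose concentration can stand in for the concentration at 24 hours. Day 15 has one. Cycle 1 Day 1 does not, and the Day -7 sample precedes any drug. A sample 24 hours after the Day 1 dose would no longer be monotherapy, because rucaparib has started by then. The schedule supports this imputation for the combination only.

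**The case against.** The strongest reply is that the plan is not tied to AUC0-5h. Section 3.3.4 allows population PK and comparison with other trials, Section 6.6 lists Cmax and Tmax and permits further parameters, and combination troughs are drawn on three days. The comparison is descriptive, with no threshold and no test. The RP2D is set mainly by DLTs, in fewer than one-third of at least 6 patients per Section 3.1.1.1, so no decision rule turns on 1.3 versus 1.5. The phrase time zero to time t already signals truncation.

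Much of that stands. It limits the consequence and makes the remedy cheap. It does not remove the problem: permission to use population PK is not a commitment to use it for this comparison, and the only AUC that Section 6.6 names is described as something the samples cannot deliver without a model.

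A reader might also infer more than the documents support: that the window captures a fixed quarter to a third of exposure, and that AUC0-5h always pulls the result toward no interaction. The share depends on a half-life and a model that the documents do not give. Section 3.3.1 speaks of CYP3A inhibition and higher exposure without saying whether clearance or bioavailability changes. Steps 4 and 5 show that the bias can vanish or reverse.

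**Conclusion.** The mismatch between label and sampling is certain from the documents alone: AUC0-t here is AUC0-5h, covering 5 of 24 hours on both comparison days.

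The size and direction of any bias are conditional. With lower systemic clearance and steady state on both days, AUC0-5h understated the ratio in every case run; the main one-compartment results are 1.26-1.47 for a true 1.5 and 1.54-1.93 for a true 2.0. The shortfall is largest at short half-lives in the one-compartment model. There is no bias if only bioavailability changes. For a 1.5-fold effect at a half-life near 48 h there is a slight overstatement, 1.53-1.55. All of these rest on assumed half-lives, absorption rates and compartment structures.

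The plan should be changed because the comparison feeds the RP2D discussion and the correction is easy. The finding does not show that the RP2D would be wrong, since PK is one input to it and not the rule.

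**What to change.** In Section 6.6:

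- Rename the non-compartmental measure AUC0-5h and drop the words total exposure.
- Pre-specify 24-hour steady-state AUC, or apparent clearance, with and without rucaparib as the interaction measure. Estimate it by the population PK analysis already allowed in Section 3.3.4, and state the model's assumptions.
- Keep AUC0-5h and Cmax as supporting measures.
- State that the 24-hour value will not be imputed from a trough for this comparison under the current schedule. Imputing it on Day 15 only would set a 24-hour AUC against a 5-hour one.

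The cost is a change of wording and a commitment to modelling already foreseen; no new sample is needed. The drawback is that the monotherapy estimate will depend on a model fitted to post-dose samples at 1-5 hours only, with no monotherapy trough. It may be imprecise, so its interval should be reported beside the point estimate.
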